**Table of protocol changes**

Versions	Dates	Changes
V1	20 DEC 2018	Initial version
V2	23 JAN 2019	Address and responsibilities - Precisions in number of patients, follow up and monitoring – Budget
V3	20 MAY 2019	Budget update - Study duration update – Precisions in chapters 1.2, 1.3, 2.2, 4.3, 5, 7.1 & 7.2
V4	15 JUL 2019	Precisions about data collection and analysis 7.1, 7.2
V5	15 OCT 2019	Precisions in data collection in chap. 4.3 and addition of visits summary table in chap 4.4, review of adverse events definitions and procedure in chap 6.
V6	06-DEC-2019	Corrections following investigators review in chap 1.3, 2.2, 2.6, 3.2, 4.3.2, 4.3.3, 4.4, 4.7, 6.1, 7.1, 7.3 and 8.1. Update of chap. 11.
V7	28-JAN-2020	Update of signatories
V8	24-FEB-2020	Extension of inclusion period
V9	04-NOV-2020	New principal investigator (2.3, 6.2.1, 12) Corrections following Ethic committee review: Update of first page with research legislation type as HRO and risk category A, 3.1, 3.2, 4.3, 4.4 (update of table of collected data), 7.1, 7.2, 7.3, 8.3, 8.4, 8.5, 8.7, 9, 11 In chap 8.3: Replacement of EU medical devices directive 93/42/EEC by the Regulation 2017/745.

## 1 INTRODUCTION

### 1.1 Background

Refractory function in patients with a cataract is mainly restored by implanting intraocular lenses (IOL) destined to replace the crystalline lens. While new surgical techniques for removing the crystalline lens have been developed, these lenses have been considerably perfected to resemble the natural crystalline lens as closely as possible.

Since December 2015, SAV-IOL SA got the CE marking with lenses which have the potential to obtain the best results in terms of visual acuity and comfort. Both are benefiting from the Instant Focus © technology (legal manufacturer SAV-IOL-SA [www.sav-iol.com](http://www.sav-iol.com))

- The lens InFo is a refractive/diffractive hybrid lens characterized by extended depth of focus to guarantee satisfactory vision, regardless of focal length and light conditions. This benefit is particularly apparent for intermediate vision, significantly improved relative to multifocal optics that only allow focus on objects in near and far vision, without any usual adverse events met with that multi/polyfocal lenses
- The lens Lucidis is a refractive lens with an extended depth of focus to get satisfactory vision, regardless of focal length and light conditions. This benefit is particularly apparent for far vision, with additional view for near and intermediate vision. Lucidis is proposed in 2 sizes : 10.8 mm (Lucidis 108M) & 12.4 mm (Lucidis 124M) diameter, containing the same optical size (6.0 mm diameter).

### 1.2 Study Rationale

The objectives of the study is to evaluate efficacy and long-term safety of the Lucidis lens. Through this PMCF (post marketing clinical follow-up), the objective is to obtain an up-to-date clinical evaluation of the medical device thus supplementing data from experimental trials. Clinical and functional changes in the implanted eyes among a patient population in which the opaque crystalline lens resulting from cataract was removed and replaced by a Lucidis IOL will be described.

The objectives involve both evaluation of changes in ocular function in terms of visual acuity and comfort and listing possible complications of surgery and adverse reactions.

Study primary objectives – measure of:

- Far Best Corrected Visual Acuity in photopic conditions
- Near, intermediate and far Uncorrected visual acuity in photopic conditions
- Far Best Corrected Visual Acuity in mesopic conditions
- Near, intermediate and far Uncorrected visual acuity in mesopic conditions

Study secondary objectives – measure of:

- Contrast sensitivity in photopic conditions
- Contrast sensitivity in mesopic conditions
- Adverse reactions.

### **1.3 Benefit risk ratio**

Contraindications for intraocular lens are previous pathologies or physiological conditions, which may be aggravated by the lens, or in cases where the lens may interfere with the possibility of examining or treating diseases.

- Acute eye diseases or external or internal infection
- Fuchs' proliferative diabetic retinopathy
- Severe corneal dystrophy
- High myopia
- Chronic or recurrent severe uveitis
- Severe optic nerve atrophy
- Congenital bilateral cataracts or non-age-related cataract
- Glaucoma
- Choroidal hemorrhage
- Color vision deficiencies
- Irregular corneal astigmatism
- Extremely shallow anterior chamber
- Severe Microphthalmos or Macrophthalmos
- Aniridia
- Retinal Detachment
- Macular degeneration
- Micropupil

Severe complications during surgery might be:

- Choroidal hemorrhage
- Vitreous loss

# Evaluation of efficacy and long-term safety for Lucidis Instant Focus© - PMCF Study protocol

Version 9 - Page 7/25

SWISS ADVANCED VISION

INTRAOCULAR LENS

Adverse reactions and complications due to, or following surgery and, implantation of any intraocular lens may include, but are not limited to:

- Increased Astigmatism
- Corneal Decompensation
- Vitritis
- Loss of Best Spectacle Corrected Visual Acuity
- Lens Dislocation
- Lens Vault
- Anterior Subcapsular Cataract
- Macular Edema
- Iritis
- Decentration/Rotation of the InFo lens
- Non-reactive Pupil
- Uveitis
- Secondary Surgical Intervention to remove/Replace lens
- Pupillary Block Glaucoma IOP > 5mmHg over baseline and IOP > 25mmHg
- Corneal Edema
- Retinal Detachment
- Corneal Endothelial Cell Loss
- Secondary Glaucoma
- Hyphema
- Synechiae to Implant
- Hypopyon
- Under/Over correction
- Severe Intraocular Inflammation
- Significant Glare and/or Halos around lights
- Intraocular Infection
- Vitreous Loss

The benefit for the patient is the treatment of its cataract and improvement of his visual acuity.

Before implanting the Lucidis lens with any of the following conditions, pre-operative evaluation should be performed by a surgeon to consider the potential benefit/risk ratio.

The patients included in this observational study are planned for surgery with Lucidis lens implantation. There is no additional risk or benefit for them participating to this post-market follow-up study.

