### 4.3.2 Data collected at baseline visit (pre-operative):

- Cataract history: age of onset, type of cataract;
- Pre-operative ophthalmological examination: standard slit-lamp examination, visual acuity in photopic and mesopic conditions (uncorrected visual acuity for near, intermediate (80cm), and far vision & best corrected visual acuity for far vision), contrast sensitivity and aberrometry.

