#### 4.3.5 Data collected after surgery (at week 1, month 1, month 6, year 1):

- Postoperative ophthalmological examination: standard slit-lamp examination, visual acuity in photopic and mesopic conditions (uncorrected visual acuity for near, intermediate (80cm), and far vision & best corrected visual acuity for far vision), contrast sensitivity, aberrometry and defocus (defocus will be measured for the first 40 patients as a minimum).
- Adverse events spontaneously reported by the patient;
- Specific interview concerning visual acuity, frequency of glare and halo, distorted vision.
- Possible postoperative complications
- Change in medication intake

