### **5 ASSESSMENT METHODS**

At each visit the patient will be seen by both an ophthalmologist and an optometrist. The qualified optometrist will carry out all examinations regarding visual acuity, contrast sensitivity and aberrometry. The investigating ophthalmologist will collect data through slit-lamp examination, and through interviewing the patient about any unusual sensations or adverse events based on the patient's impressions, observations and response to the question: "How are you feeling?" or "How have you felt since the last visit?". Adverse events will be recorded. An anomaly persisting at the end of the study will be monitored by the investigator until they resolve or at least stabilize.

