### **6.1.3 Severity of the adverse event**

The severity of the adverse event should be based on the following classification:

- mild: generally transient, does not affect the patient's normal daily activities;
- moderate: interferes with the patient's daily activities and/or sleep;
- severe: prevents the patient's daily activities and/or sleep.

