### 7.2 Statistical analysis

The analysis will be comparative and shall concern all patients having agreed to take part in the study. Statistical data will be evaluated for each eye, additionnaly in case of bilateral surgery visual acuity for both eyes will be analysed for each eye and together. The quantitative variables will be described in terms of sample size, mean, standard deviation, median, range and missing data. The qualitative variables will be described in terms of sample size, percentage and missing data. Two-sided 95% confidence intervals will be provided if the endpoint is considered relevant. Wilcoxon and Student significance tests will be used.

An interim statistical analysis will be performed from the 6 months data of all included patients. A final statistical analysis will be performed after the last 1-year follow-up visit of the last patient. Data will be compared to the state of the art data regarding similar lenses available on the market.

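### Loss of best corrected acuity is a named adverse reaction and is measured per eye, but the plan neither defines a loss nor counts the eyes that have one

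*Combined protocol and SAP*

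**What the plan says.** **The harm.** Section 1.3 lists "Loss of Best Spectacle Corrected Visual Acuity" among reactions that may follow surgery and implantation of any intraocular lens. It gives no size of loss and no reference visit.

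**The measurement.** The first primary objective in 1.2 is "Far Best Corrected Visual Acuity in photopic conditions"; adverse reactions are a secondary objective. Section 4.3.2 records "best corrected visual acuity for far vision), contrast sensitivity and aberrometry" before surgery. Section 4.3.5 repeats the measurement at Week 1, Month 1, Month 6 and Year 1: "Postoperative ophthalmological examination: standard slit-lamp examination, visual acuity in photopic and mesopic conditions". At Day 1 it is at the investigator's discretion (4.3.4 and the table in 4.4), and 4.3.3 lists no acuity on the day of surgery. One case report form is completed per eye (4.3, 7.1).

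**Safety capture.** Section 4.3.5 lists "Adverse events spontaneously reported by the patient", and separately a specific interview that covers acuity and an item for postoperative complications. Under section 5, "The qualified optometrist will carry out all examinations regarding visual acuity, contrast sensitivity and aberrometry", while the ophthalmologist performs the slit-lamp examination and interviews the patient. The definition in 6.1.1 admits any unfavourable sign.

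**The analysis.** Section 7.2 states: "The quantitative variables will be described in terms of sample size, mean, standard deviation, median, range and missing data". It adds Wilcoxon and Student tests, and confidence intervals where the endpoint is considered relevant. Percentages are planned for qualitative variables only, and acuity loss is not set up as one.

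**The concern.** The study is meant to describe long-term safety, and the Month 6 and Year 1 visits were added to routine care for it. A small number of eyes that recover well by Month 1 and then lose best corrected acuity is the kind of late signal those visits could show. The data to identify such eyes will exist, but the planned outputs do not ask how many there are.

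Two links are missing. First, the optometrist measures acuity and the ophthalmologist collects adverse events, and no step makes a measured drop prompt a safety review. Second, the analysis of acuity rests on averages and spread. Against baseline, the gain from cataract removal in most eyes will swamp losses in a few. Against Month 1, a few losses barely move the mean. The report could therefore describe good average acuity and an adverse-event list without giving the rate of a harm that the protocol itself names.

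Section 7.3 says 100 eyes suffice to detect post-operative complications. For this complication, detection needs a case definition and a count.

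**Working it through.** **The plan's own figure.** Section 7.3 gives 100 eyes as sufficient and 120 to be included, without a complication rate, detection probability, SD or alpha. The figure cannot be reproduced from the documents. For orientation, P(at least one event) = 1 − (1 − p)^n. For n = 100 this is 63.4% at p = 1%, 86.7% at 2% and 95.2% at 3%. Those probabilities apply only if an event is recognised when it happens.

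**Inputs.** From 2.2: 120 eyes in 60 to 120 patients. Assumed, because the documents give none of them: acuity in logMAR, SD of within-eye change 0.10 (range 0.08 to 0.15), losses of 0.2 or 0.3 logMAR, 3 or 6 affected eyes, eyes independent, two-sided 5% tests. Section 7.2 does not name a Month 1 to Year 1 comparison, so the first calculation shows how such a test would behave if run.

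**1. Late loss, Month 1 to Year 1**
- Mean shift = k × 0.3 / 120, which is 0.0075 logMAR for k = 3 and 0.015 for k = 6.
- 95% CI half-width = t(119) × SD / √120 = 1.980 × 0.10 / 10.954 = 0.018. For SD 0.08 it is 0.014, and for SD 0.15 it is 0.027.
- Simulation: 120 changes drawn from N(0, 0.10), with 0.3 added in k eyes.

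| Affected eyes | Student p<0.05 | Wilcoxon p<0.05 |
|---|---|---|
| 3 of 120 (2.5%) | about 9% | about 6 to 7% |
| 6 of 120 (5%) | about 24% | about 12 to 13% |

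With 3 affected eyes, the Student figure runs from about 11% at SD 0.08 to 6 to 7% at SD 0.15. These rates are little above the 5% expected with no loss at all.

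**2. Loss against baseline**
- Suppose 6 eyes lose 0.2 and 114 gain 0.3. Mean gain = (114 × 0.3 − 6 × 0.2) / 120 = 33.0 / 120 = 0.275, against 0.300 with no losses.
- With SD 0.1 among the gaining eyes, the 95% CI is 0.249 to 0.301 and mean/SE is 20.6. With SD 0.2, it is 0.235 to 0.315 and 13.5.
- With an effective sample of 60, the ratio is still 14.6 or 9.5. The test stays strongly favourable.

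**3. What a count would give** (exact two-sided 95% intervals, eyes independent)
- 0/120: upper limit 3.0%
- 3/120: 2.5% (0.5% to 7.1%)
- 6/120: 5.0% (1.9% to 10.6%)
- If two eyes of a patient carried no separate information, 0/60 would give an upper limit of 6.0%.

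**4. False flags from measurement noise.** Take a threshold of 0.2 logMAR worse than Month 1 and no true change.
- One visit, SD 0.10: P(Z > 0.2/0.10) = 2.3%, or 2.7 of 120 eyes.
- Either Month 6 or Year 1, with equal independent visit errors and a shared Month 1 value (correlation of the two changes 0.5): about 5 of 120. For SD 0.08 it is about 1, and for SD 0.15 about 18.
- Both visits, SD 0.10: 2 × 2.73 − 4.97 = about 0.5 of 120.

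An unconfirmed single-visit rule would thus flag more unchanged eyes than the 3 true losses assumed in step 1. Requiring the drop at both visits removes most of them.

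**The case against.** The strongest reply is that the safety net is wider than patient report and already admits a measured loss. Slit lamp is scheduled from Week 1 onwards, there is a complications item independent of what the patient volunteers, the interview asks about acuity, the adverse-event definition covers any unfavourable sign, and 6.2.2 requires non-serious events on the form whatever their cause. The patient sees both optometrist and ophthalmologist at each visit. All of this stands. It shows that a loss may be recorded, not that it must be, and it produces no count.

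A reader might go further in four ways that the documents do not support:
- *Acuity is taken at every scheduled visit.* Day 1 is discretionary and the day of surgery has no acuity item. This does not matter for a comparison of Month 6 and Year 1 with baseline or Month 1.
- *Safety depends on what patients report.* The inputs above contradict this.
- *Losses would be hidden.* Data are kept per eye, the sponsor reviews the forms, and 7.2 includes SD and range. If the range is taken on change, it shows the worst eye: with 3 losses of 0.3 and SD 0.10, the median worst change is about 0.38, against 0.25 with none. A range does not show how many eyes lost acuity, and a range of visit values need not show loss at all. The losses are uncounted, which is the narrower claim.
- *The severity scale cannot grade a lasting one-eye loss.* Section 6.1.3 says "mild: generally transient", which does not exclude a lasting mild event. Lasting disability is a seriousness criterion in 6.1.1, and section 5 has persisting anomalies followed until they resolve or stabilise. That the fellow eye would drive the grade is inference.

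It is also fair that 1.3 is a general list of risks, not a list of endpoints, and that the magnitudes rest on assumed values.

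**Conclusion.** The point holds as a gap in definition and analysis. A named harm can be read per eye from data already planned, yet the plan contains no threshold, no reference visit, no link from a measured loss to adverse-event review, and no count.

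The size depends on assumptions about SD, loss and number of eyes that the documents do not supply, and on treating eyes as independent. Across SD 0.08 to 0.15 the conclusion is stable: with 3 of 120 eyes losing 0.3 logMAR, the mean shift of 0.0075 stays inside a half-width of 0.014 to 0.027. It does not follow that the plan excludes such losses from safety or conceals them. The change should be made because it is cheap and serves the stated long-term safety objective.

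**What to change.** Add to 7.2:
- The number and percentage of eyes whose far photopic best corrected acuity at Month 6, and at Year 1, is worse by a prespecified amount than (a) baseline and (b) Month 1. For example, use 0.2 logMAR, with 0.3 as a sensitivity threshold. State the acuity unit.
- 95% confidence intervals that allow for two eyes per patient.
- Separate lines for losses present at both Month 6 and Year 1 or explained by a recorded finding, and for unconfirmed single-visit drops.
- A listing of each flagged eye with its slit-lamp findings.

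Add to section 5 or 6 that the investigator reviews each flagged eye as a possible adverse event, whether or not the patient reported it, and records the decision. Entry should not be automatic, because noise flags would contaminate the safety listing. The severity scale need not change.

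**Cost.** One derived table, one listing and a review step, with no new measurement or visit. Some flags will be noise: about 5 of 120 unchanged eyes across the two visits against Month 1 at SD 0.10, and about 1 to 18 for SD 0.08 to 0.15.

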## 2 STUDY DESIGN

### 2.1 Project title

Evaluation of efficacy and long-term safety of Lucidis Lenses / PMCF.

### 2.2 Study design

This is a monocentric, longitudinal, prospective, cohort study for a population of 120 eyes on 60 to 120 patients (depending on mono or bi-lateral surgery conditions) with a cataract, receiving an Lucidis lens implant. After the cataract procedure, data collection will take place during appointments planned by the physician (after one day, one week, one month, six months and one year).

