### 3 SELECTION OF PATIENTS

#### 3.1 Patient selection method

Once the study has been initiated, the investigator will recruit the 60 to 120 patients (120 eyes) in an expected period of 6 months. The inclusion period will end at the inclusion of the last patient.

During this period, the investigator will invite all patients for whom the decision has been made to implant a Lucidis lens to take part in the study, so as to include all patients fulfilling the study inclusion criteria in a consecutive manner.

Prior to inclusion and before carrying out any study-related procedures, the investigator will first inform each patient of the study objectives, the conditions for their participation in the study, and the need to allow the study monitor to have direct access to their medical records. Patients will be given an information leaflet and informed consent form, which they are required to personally date and sign.

Before implanting the Lucidis lenses with any of the following conditions, pre-operative evaluation is performed by the surgeon to consider the potential benefit/risk ratio. In case of contraindications, ie the patient already has pathologies or physiological conditions, which may be aggravated by the lens, or in cases where the lens may interfere with the possibility of examining or treating diseases, the lens will not be implanted and the patient will not be included in the study.

Additionally to exclusion criteria, the risk/benefit ratio is individually assessed for each patient with regards to safety and patient vision performance expectations. Diagnostic, anamnesis, eye biometry combined with way of life and patient expectations are considered prior the selection by the surgeon or proposal to the patient to implant a Lucidis IOL. Lucidis is an EDOF (Extended Depth Of Focus) intraocular lens that provides near and intermediate vision in addition to distance vision. Should a patient's medical status or visual expectations determined as not in adequacy with the device, alternative available devices - such as monofocal or multifocal intraocular lenses would be implanted instead. The choice of the intraocular lens based on the state of the art is an essential parameter evaluated in depth by the physician (through diagnosis, anamnesis, comorbidities, biometry, lenses optical performances, dysphotopsia, patient way of life and expectations, etc.).

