#### 3.2 Selection Criteria

- adult patients (≥18 years)
- having agreed to take part in the study and complete post-operative follow-up requirements (by having signed the information leaflet-informed consent form);
- significant reduction in visual acuity and/or visual comfort from cataract;

- for whom the physician made the decision to implant a Lucidis based on medical considerations.

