## **4 PRACTICAL IMPLEMENTATION OF THE STUDY**

This study does not affect the physician-patient relationship, or usual patient management. The physicians remain free in their prescribing and follow-up practices; no specific procedures or examinations are requested. The study remains within the normal treatment context.

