### 4.3.1 Data collected at inclusion:

- Date of inclusion;
- Verification of inclusion and exclusion criteria;
- Declaration by the physician that the patient has signed the information leaflet and informed consent form;
- Demographic data (age at inclusion, gender);
- Candidate eye for operation (uni- or bilateral in nature)

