### 4.4 Evaluation schedule

The initial evaluation during the inclusion and baseline visit is done from 1 to 14 days before the date of surgery.

The evaluation schedule will then correspond as follows, for each eye:

- Day of surgery
- Day 1 (0 to 3 days after surgery)
- Week 1 (7 to 10 days after surgery)
- Month 1 (30 to 45 days after surgery)
- Month 6 (180 to 195 days after surgery)
- Year 1 (360 to 390 days after surgery).

If it is not possible to perform a visit, it must be documented and justified on the p-CRF. See also chapter 4.5 for lost patients follow-up.

Evaluation of efficacy and long-term safety for Lucidis  
Instant Focus© - PMCF Study protocol

Version 9 - Page 13/25

SWISS ADVANCED VISION

INTRAOCULAR LENS

In case of bilateral surgery, the Month 6 and Year 1 follow-up visits of each eye can be combined together into 1 visit, if within the timeframe. After the second eye's surgery, visual acuities are additionally measured as bilateral.

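### With no rule for second-eye entry and no allowance for pairing, per-eye results may favour the lens if a second eye's entry depends on the first eye's result

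*Combined protocol and SAP*

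**What the plan says.** The protocol counts eyes. Section 2.2 plans "120 eyes on 60 to 120 patients (depending on mono or bi-lateral surgery conditions" and leaves the mix of one-eye and two-eye patients open. Section 7.2 states "Statistical data will be evaluated for each eye", names Wilcoxon and Student tests, and adds a joint analysis of acuity after bilateral surgery. It has no first-eye or patient-level analysis.

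Entry is defined by patient. Section 3.2 admits patients "for whom the physician made the decision to implant a Lucidis based on medical considerations", and under section 3.1 "the investigator will invite all patients for whom the decision has been made to implant a Lucidis lens to take part in the study". Neither section has a criterion for a second eye. Section 4.3.1 records "Candidate eye for operation (uni- or bilateral in nature" at inclusion, before any surgery.

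The two eyes are operated on separately. Section 4.4 sets the visit schedule for each eye and notes "After the second eye's surgery, visual acuities are additionally measured as bilateral". It gives no minimum or maximum interval between surgeries. Sections 4.3.4 and 4.3.5 ask about glare, halo and distorted vision at Day 1 and from Week 1 on.

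Lens choice is not fixed by the study. Section 4 says "The physicians remain free in their prescribing and follow-up practices". Section 3.1 says that where status or expectations do not suit the lens, "alternative available devices - such as monofocal or multifocal intraocular lenses would be implanted instead", and lists dysphotopsia among the factors weighed.

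**The concern.** In a per-eye analysis a patient's weight is the number of eyes entered. If patients whose first eye did poorly are less likely to have a second Lucidis, they count once, while those who did well count twice. Means and percentages would then move in the lens's favour. Section 7.2 compares the results with state-of-the-art data on similar lenses, so such a drift would carry into that comparison. Glare and halo are the most exposed, because they can be known early and bear directly on lens choice.

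A second problem does not depend on any selection. Student and Wilcoxon tests treat eyes as independent, and two eyes of one patient are not.

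**Working it through.** **The plan's own figure.** Section 7.3 plans 120 eyes and considers 100 sufficient, but gives no event rate, effect, SD, power or dropout, so neither number can be reproduced. As a plausibility check only: 100 independent eyes have a 95% chance of showing at least one event at a rate of 1 − 0.05^(1/100) = 2.95%.

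**Can the first eye's result be known in time?** Combining late visits (section 4.4) is optional. The Month 6 window of 180–195 days implies surgeries at most 15 days apart when those visits are combined; the Year 1 window of 360–390 days implies at most 30. The first eye's Day 1 and Week 1 (days 7–10) assessments fit inside 15 days. So the result can be known, but the protocol does not say that it is used.

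The rates, entry probabilities, correlations and SDs below are assumptions, because the documents give none.

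**Glare/halo as a yes/no outcome.** Let p be the first-eye prevalence, a and b the probabilities that a second eye enters without and with first-eye symptoms, and r the between-eye correlation. The second eye has symptoms with probability p + r(1−p) if the first does, and p(1−r) if not. Then

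per-eye prevalence = [p + p·b·(p + r(1−p)) + (1−p)·a·p(1−r)] / [1 + p·b + (1−p)·a].

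With p = 0.20 and a = 0.80:

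| b | r = 0.5 | r = 1.0 |
|---|---|---|
| 0.8 | 20.0% | 20.0% |
| 0.6 | 19.1% | 18.2% |
| 0.4 | 18.1% | 16.3% |
| 0 | 16.1% | 12.2% |

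For example, b = 0 and r = 1 give 0.20/(1 + 0.64) = 12.2%. The worst case (a = 1, b = 0, r = 1) reduces to p/(2−p) = 0.2/1.8 = 11.1%. First eyes alone return 20% in every row. The bias is also zero if r = 0.

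**Mean acuity, in SD units (higher is worse).** If the worst 20% of first eyes never lead to a second Lucidis eye and all others do, the per-eye shift is −ICC × 0.280/1.8, where 0.280 is the standard normal density at the 80th percentile. This gives −0.047, −0.078 and −0.124 at ICC 0.3, 0.5 and 0.8; a simulation of 2,000,000 patients gave −0.046, −0.078 and −0.125. With graded entry (80% at the average first eye, odds falling 1.5- to 4-fold per SD worse) the shift is −0.010 to −0.094. At an assumed SD of 0.10–0.15 logMAR, 0.125 SD is 0.013–0.019 logMAR.

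**What removes the shift.** First eyes alone do. So does a likelihood-based paired-eye model when entry depends on the observed first-eye result: simulating 200,000 patients under the worst-20% rule, the naive shift was −0.048, −0.077 and −0.123 SD at the three ICCs, and the likelihood estimate was within 0.002 SD of the truth each time. Correcting only the standard error leaves the point estimate where it was.

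**Pairing, regardless of selection.** For 120 eyes from 60 patients the design effect is 1 + ICC. The effective number of eyes is 120/1.3 = 92, 120/1.5 = 80 and 120/1.8 = 67. Intervals that ignore pairing are too narrow by √(1 + ICC) = 1.14, 1.22 and 1.34.

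**The case against.** The case against a bias is substantial.

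- **A fresh lens choice is not in the text.** A reader might infer that a second eye enters only if the surgeon chooses Lucidis again after seeing the first result. No section says so. The alternative-lens sentence in 3.1 concerns selecting the patient in the first place, laterality is recorded before surgery, and the combined visits foresee closely spaced operations. Many bilateral cases may be planned at the outset. This stands. It makes the bias possible, not established.
- **The selection would not be invisible.** A reader might infer that it could never be detected. In fact candidacy (4.3.1), operated eye and lens (4.3.3) and a separate p-CRF per eye (4.3, 7.1) identify a bilateral candidate with only one study eye. Only an explicit field for the second eye's fate and the reason is lacking.
- **Per-eye averages may be the target.** Section 1.2 speaks of changes in implanted eyes, and for that average the per-eye mean is correct. This stands for description. It does not serve a comparison with other lenses, where patients should not be weighted by their own outcome.
- **First eyes alone would weaken safety.** They could number 60, below the 100 in section 7.3. At an assumed 3% event rate, the chance of at least one event is 1 − 0.97^60 = 84%, against 1 − 0.97^100 = 95%. This stands and shapes the fix.

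**Conclusion.** The concern holds in conditional form. The protocol has no rule for second-eye entry, leaves lens choice free, can have the first eye's result before the second operation, and analyses per eye with tests that ignore pairing. If entry depends on the first eye's result and fellow eyes are positively correlated, the results favour the lens.

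The size is unknown. On the assumed inputs, a true 20% glare/halo prevalence reads as about 12 to 19%, with 11% as the worst case. The largest acuity shift in the scenarios run is about 0.13 SD, which is small. Both are zero if entry is unrelated to the first result. The stronger statement, that per-eye results do overstate acuity and tolerance, is not supported.

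The neglect of pairing does not depend on selection. It applies whenever both eyes of some patients are analysed together and their outcomes are correlated.

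**What to change.** In section 7.2:

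- For acuity, contrast sensitivity and glare/halo, make the main analysis either the first-operated eye of each patient or all eyes in a likelihood-based model with a patient random effect. The first option needs no assumption about why second eyes enter. The second keeps all eyes but relies on entry depending on results that are in the model.
- Show first-eye, second-eye and binocular results separately.
- Keep every implanted eye in the adverse-reaction analysis, with first-eye rates alongside, so that the 100-eye basis in section 7.3 is preserved.

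On the p-CRF of each bilateral candidate, record whether the second eye received Lucidis, another lens or no surgery, with the reason. Report that proportion, and compare first-eye results by whether a second eye entered. This records the lens choice and does not constrain it.

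The cost is a few sentences in 7.2, one p-CRF item and somewhat wider intervals for acuity and contrast. Part of that widening only corrects intervals that pairing would have made too narrow. No extra visits or patients are needed.
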